Homework: Group Individual Psychotherapy PT	8/10 practice sessions 4/5 trauma rehearsals 2/2 weekend flowsheets	Give opportunity for practice/trauma rehearsal before class

Study interventionists will maintain study activity logs (see **Appendix E**, maintained centrally by the Study Coordinator) where they will log the date and completion status of each clinical activity (including sessions attended or missed). These will be brought to weekly interdisciplinary staffing meetings where adherence will be discussed and problem-solved by the interdisciplinary treatment. The PI will attend parts of these meetings to monitor study progress and troubleshoot general problems (he cannot stay when specific patients are discussed, even by study ID, because he

would become aware of which IDs are in the FORT-A group). A study activity log example is below:

FORT-A; Week 1				
ID	Date	Activities	Attended?	Notes
10EX1	01/01/2001	Group PT IP	Y Y Y	Patient reported an injury on 01/02/2001; entered in AE log as non-study-related; consulted study MD on 01/05/2001; pt was cleared to continue
	01/02/2001	Group PT BFB	Y Y Y	
	01/03/2001	---- Rest Day ----		
	01/04/2001	Group PT IP	Y N Y	Patient given an extra flowsheet for the evening of 01/05/2001 to make up that missed session; BFB missed on 01/05/2001 and was rescheduled for next week
	01/05/2001	Group PT BFB	Y N N	

Participant adherence to assessments. Adherence to assessments is vital to this work. For this research, assessment is broken into 3 distinct categories (psychosocial, functional, opioid). Most assessments are administered at pre-treatment, post-treatment, 6-month follow-up, and 12-month follow-up. A few measures are ongoing. Adherence to assessment is defined as completion of assessments within a specified window of time. Categories of assessment, assessment windows, and managing adherence to assessments are as follows:

FORT-A Assessment Category	Assessment Window	Tips to Promote Adherence
Psychosocial Assessments	Pre-treatment/Baseline * ≤ 2 weeks before treatment	Schedule pre- and post-tx assessment with first and last days of tx
Functional Capacity Assessments	Post-treatment * ≤ 2 weeks after Tx completed	
Opioid Assessments	6-month follow-up *24 weeks (± 2 weeks) after Tx completed	Reminder/check in phone calls every month
	12-month follow-up *50 weeks ± 2 weeks after Tx completed	Psychosocial and FCE scheduled on same day

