Ongoing Assessments	MEMS/Actiwatch – Start at pre-treatment and end at 12-month f/u TLFB/MQS – Administered at pre- and post-treatment and every month after post-treatment.	
----------------------------	---	--

Study evaluators will maintain active logs for assessments identifying participants by unique ID # only and including date of evaluation, whether or not evaluation was in a study window, if PI approved out of window assessment (when outside of a window), whether an AE was identified in the assessment (e.g., suicidal ideation on the PHQ-9 item #9), and notes about assessment (see **Appendix F**). These logs will be monitored by the PI and coordinator weekly to ensure that assessments are completed on time. An example assessment log is as follows:

ID	Assessment	Assessment Domains	Assessment Date	Window? (Approved?)	Notes
10EX1	Pre-Treatment * within 2 wks before tx phase	Psychosocial	01/01/2001	Y	Treatment Phase Start 01/04/2001 End 01/25/2001 10EX1 forgot MEMS and Actiwatch at Post-Tx; PI approved out of window download; we can use data up to 01/25/2001 10EX1 sustained injury playing basketball on 07/20/2001; not cleared for FCE for 3 months; PI denied out of window assessment due to injury delay 10EX1 completed FCE on 01/24/2002 but not time for testing; r/s for when returns from vacation (01/24); PI approved out of window
		FCE	01/01/2001	Y	
		TLFB	01/01/2001	Y	
		MEMS	01/01/2001	Y	
		Actiwatch	01/01/2001	Y	
	Post-Treatment * within 2 wks after tx completed	Psychosocial	01/25/2001	Y	
		FCE	01/25/2001	Y	
		TLFB	01/25/2001	Y	
		MEMS	02/10/2001	N (Y)	
		Actiwatch	02/10/2001	N (Y)	
	6-Month *24 weeks ± 2 weeks after tx completed	Psychosocial	07/22/2001	Y	
		FCE	---	N (N)	
		TLFB	07/22/2001	Y	
		MEMS	07/22/2001	Y	
		Actiwatch	07/22/2001	Y	
	12-Month *50 weeks ± 2 weeks after tx completed	Psychosocial	02/07/2002	N (Y)	
FCE		01/24/2002	Y		
TLFB		02/07/2002	N (Y)		
MEMS		01/24/2002	Y		
Actiwatch		01/24/2002	Y		

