6.2.4 Followup Visits (see Figure 4)

Follow-up assessments will occur in the following intervals:

Visit	Measure	Assessment Window
Visit 2 (Baseline)	Psychosocial Assessment Pain Diary Functional Capacity Evaluation (FCE) Upload Actiwatch Provide and Train for MEMS Adverse Events Opioid/Medication Assessments (TLFB/SOWS/COMM/Concomitant Medications) MQS STRONG STAR Common Data Elements	≤ 2 weeks before treatment
Visit 14 (Post-Treatment)	Psychosocial Assessment Pain Diary FCE	≤ 2 weeks after treatment

	Upload Actiwatch Upload MEMS Adverse Events Opioid/Medication Assessment MQS STRONG STAR Common Data Elements	
Phone Assessments 1-11	Opioid/Med Assessment (TLFB) MQS	Monthly ± 1 week
Visit 15 (Six-Month Follow-Up)	Psychosocial Assessment Pain Diary FCE Upload Actiwatch Upload MEMS Adverse Events Opioid Assessment/Medication MQS STRONG STAR Common Data Elements	± 24 weeks after treatment ± 2 weeks

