9.5.2 Secondary Outcomes

There are numerous secondary outcomes for this study that can be meaningfully categorized as physical measures (functional capacity evaluation, Actiwatch), medication (MEMS, timeline followback interview, MQS), psychosocial pain (Pain Catastrophizing Scale) and psychosocial trauma and emotional distress (measures of PTSD, depression, suicide risk, etc.). Because these measurement categories all require separate skillsets for interpretation of problematic or ambiguous results, they must all be adjudicated through separate subcommittees within the study team and the STRONG STAR Consortium as follows:

Physical Measures will be adjudicated by the PI, the Research Coordinator, and [name] (an internationally-recognized expert in Physical Therapy assessment for chronic pain) or a PRC PT/OT. Functional Capacity Evaluation (FCE) data will be recorded by UTHSCSA PT students and/or PRC PT/OT providers and will be discussed with [name] or a PRC PT/OT within two business days after each assessment. Data will be scrutinized by [name] or a PRC PT/OT in raw format and interpretations will be recorded. Any ambiguity in the data will be adjudicated by an assessment sub-committee including the PI, the PT Interventionist(s), and [name] OR a PRC PT/OT. Data will be examined and discussed using unique identifiers only. Actiwatch data will be uploaded by a STRONG STAR IE at pre-treatment and all follow-up assessments and uploaded data will be scrutinized by the IE (who will be trained in the use of the Actiwatch system by the PI – with consultation from the manufacturer if needed) who will identify any aberrations in data that may require adjudication. Actiwatch data will be adjudicated using the same timeframe, methods, and subcommittee as the PT data.

NOTE: Actiwatch was chosen over Actical for this research based on data suggesting that actigraphy offers usable data after 10 days of wear time (Freedson, 2014; Mailey et al., 2014) and that wrist-worn actigraph is more sensitive to intensity of movement

than hip-worn actigraph (Mendoza et al., 2014). Thus, we will use the Actiwatch in 10-day epochs (participants will be asked to wear them for 12 or more hours per day; per Hermann et al., 2012) at every assessment period (instead of continuous wear for 6-months at a time). Previous studies have shown higher rates of adherence using 10-day epochs.

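### The 10-day Actiwatch epoch is not anchored to the three-week program, so the FORT-A post-treatment reading can fall wholly inside treatment

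*Combined protocol and SAP*

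**What the plan says.** All references are to the combined protocol and SAP.

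- **Role of the measure.** The baseline table in 6.2.2 labels Actiwatch a Hypothesis 2 endpoint. Hypothesis 2 (1.1) covers short- and long-term follow-up. Section 9.1, under the tertiary hypotheses, puts Actiwatch into the polynomial trajectory models.
- **Epoch.** Section 9.5.2: "we will use the Actiwatch in 10-day epochs", with one epoch "at every assessment period (instead of continuous wear for 6-months at a time". On daily wear it adds that "participants will be asked to wear them for 12 or more hours per day".
- **Upload.** Section 9.5.2: "Actiwatch data will be uploaded by a STRONG STAR IE at pre-treatment and all follow-up assessments". The visit table in 6.2.4 lists "Upload Actiwatch" at Visit 2 (baseline) and again at post-treatment and six months; 6.2.5 does the same at one year.
- **Visit timing.** Baseline may be up to two weeks before treatment and post-treatment up to two weeks after it (5.4, 6.1, 6.2.4). The adherence tips in 5.4 add: "Schedule pre- and post-tx assessment with first and last days of tx".
- **Example log (5.4).** Treatment runs 01/04/2001 to 01/25/2001, and the post-treatment visit is on 01/25. The Actiwatch was not downloaded until 02/10/2001, and the note reads: "PI approved out of window download; we can use data up to 01/25/2001".
- **Start and stop.** The ongoing-assessments row in 5.4 says: "MEMS/Actiwatch – Start at pre-treatment and end at 12-month f/u". The schedule in 6.1 marks no Actiwatch at screening.

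**The concern.** An activity monitor measures what a participant does on the days it is worn. If those days are program days, the FORT-A reading includes the walking, exercise and travel that attendance itself requires. FORT-A participants attend four days a week for three weeks. Usual-care participants get no second physical therapy recommendation (5.1.1). They may still attend physical therapy, but not on a fixed schedule that matches.

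A post-treatment contrast built on such days would partly measure delivery of the intervention and report it as outcome. The post-treatment point also enters the trajectory models in 9.1. An inflated value there would bend the fitted curve and could show up as a later decline that is only the end of the program. The plan does not exclude this, and its own scheduling advice leads towards it.

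**Working it through.** The plan gives no power, effect size or analysis window for Actiwatch, so there is no stated figure to reproduce. The check is a calendar count.

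**Inputs.** The epoch is 10 days with at least 12 hours of wear a day (9.5.2). The program has 12 sessions of 90 minutes, four a week for three weeks (5.1). Sessions are taken as Monday, Tuesday, Thursday and Friday, the pattern that 5.2 reports from the original FORT trial; its use here is an assumption. The post-treatment visit falls 0 to 14 days after treatment (5.4).

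**Set-up.** Call the first Monday day 1 and the third Friday day 19. Sessions fall on days 1, 2, 4, 5, 8, 9, 11, 12, 15, 16, 18 and 19. Minimum wear per epoch = 10 × 12 × 60 = 7,200 minutes. For a visit *k* days after the last session, a look-back epoch ending on the visit day covers days 10 + *k* to 19 + *k*.

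**Visit on the last treatment day (*k* = 0).** The epoch is days 10 to 19, all within the program. It contains the sessions on days 11, 12, 15, 16, 18 and 19, so 6 of 12. Session time = 6 × 90 = 540 minutes, and 540 / 7,200 = 7.5%.

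**Across the permitted window:**

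| Days after last session | Program days in epoch | Sessions | Session minutes | Share of 7,200 |
|---|---|---|---|---|
| 0 | 10 | 6 | 540 | 7.5% |
| 3 | 7 | 4 | 360 | 5.0% |
| 7 | 3 | 2 | 180 | 2.5% |
| 9 | 1 | 1 | 90 | 1.25% |
| 10–14 | 0 | 0 | 0 | 0% |

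Of the 15 permitted visit days, 10 (offsets 0 to 9) catch at least one program day and 5 are clean. If the epoch ends the day before the visit, it is clean only from offset 11.

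**Example log.** The ten days ending 01/25/2001 are 01/16 to 01/25, all inside 01/04 to 01/25. The download came 16 days after treatment ended, yet the note stops the usable data at the last treatment day.

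**Baseline, both wear directions.** Looking back from Visit 2, the epoch contains no session, or one if the visit is on treatment day 1. Looking forward from Visit 2 with the log's dates (visit 01/01, treatment start 01/04), the epoch is 01/01 to 01/10, and 7 of its 10 days (01/04 to 01/10) are in treatment. The upload entry at Visit 2 supports looking back. The start-at-pre-treatment row in 5.4 and the absence of an Actiwatch mark at screening in 6.1 point the other way.

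**With dated epochs.** Ten days starting the day after the last session are days 20 to 29, offsets 1 to 10. They contain no program day and fit the 14-day window.

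**The case against.** The strongest reply is that first- and last-day scheduling is only a tip. The binding window is two weeks, and the Précis and 6.1 place the post-treatment assessment in Week 4/5, after a program that 4.1 puts in Weeks 1–3. This stands in part: a reader might infer that every FORT-A post-treatment epoch includes program days, and the documents do not support that. But the week label does not remove the problem. On the same calendar, Week 4 is days 22 to 28, offsets 3 to 9, and every look-back epoch from those visits still holds 1 to 7 program days. Only Week 5 visits are clean.

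A reader might also infer that baseline and post-treatment are both contaminated. They need opposite wear directions. Looking back affects post-treatment and leaves baseline essentially clean; looking forward does the reverse. At Visit 2 the plan uploads the Actiwatch but only then issues the MEMS cap, which suggests that the watch was already in use. So baseline is conflicting text, not a demonstrated bias.

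The 540 minutes cannot be read as exercise time. Each session includes a presentation or didactic part (5.1, 5.2), so 540 minutes and 7.5% are upper bounds on supervised exercise in those sessions. They are shares of wear time, not of measured activity. Program days also include group and individual sessions that may be sedentary, so a bias towards FORT-A is plausible but not shown. Weekend home exercise (5.4) is not counted.

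Finally, the log is illustrative, with invented dates, and its note covers MEMS and Actiwatch together without mentioning a ten-day epoch. It shows how staff might apply the rule, and is not proof of practice.

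**Conclusion.** The point holds for the post-treatment epoch. Nothing fixes the ten days relative to the program. Under the natural reading of upload at the visit, following the plan's own scheduling tip puts the FORT-A epoch wholly inside treatment: 6 of 12 sessions, at most 7.5% of minimum wear time. Under that reading, 10 of the 15 permitted visit days overlap the program to some degree. The short-term Actiwatch contrast and the post-treatment point in the trajectory model can therefore reflect attendance instead of carried-over activity.

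This rests on three assumptions: wear precedes the visit, the original trial's weekday pattern applies, and the epoch ends on the visit day.

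The scope is one secondary measure at one time point, plus a conflict in the baseline wording. A reader might extend the point to long-term results or to the main conclusion. The documents do not support that: the 6- and 12-month epochs lie months after the program, and the ODI analysis and sample size do not use Actiwatch. The change is still worth making, because a definition that fits the existing window removes the overlap.

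**What to change.** In 6.1, 6.2.4 and 9.5.2, define the epochs by date:

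- Post-treatment: the 10 days starting the day after the last treatment session, within the existing two-week window.
- Baseline: 10 days ending before the first treatment day, with a named visit at which the watch is issued.
- Usual care: matching dates for the corresponding cohort, so that both arms are measured over the same interval.

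In 5.4, exempt Actiwatch from the first- and last-day scheduling tip and correct the example log so that it no longer cuts the data off at the end of treatment. Reconcile the ongoing-assessments row, which reads as wear from pre-treatment through 12 months, with the 10-day epochs in 9.5.2.

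The cost is protocol wording and logistics. The watch must be issued before Visit 2, which the four-week screening window in 6.1 allows if at least 10 days are left for wear before the upload. It must then be returned or mailed back after the post-treatment visit, with some risk of late or lost devices. No new device, measure or participants are needed.

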3. STUDY DESIGN

To address the primary and secondary hypotheses, this research study was designed as a randomized clinical trial comparing the manualized FORT-A treatment to treatment as usual for polytraumatic chronic musculoskeletal pain in the STVHCS Polytrauma Rehabilitation Center. Eligible OEF/OIF/OND Veterans will be randomized to either arm in 1:1 random permuted block randomization with no stratification. Because the FORT-A is a group intervention, it is vital that we randomize into meaningful blocks of at least three Veterans and no more than seven. Three is chosen as the lower block boundary because the PI had success in the original FORT trial with FORT groups of three active duty service members. Seven Veterans will be the upper boundary because FORT groups of more than seven military members were difficult to manage. In block randomization with static boundaries, study staff overseeing randomization will lose blinding if they are aware of how many participants have already been randomized into each block. For example, if block boundaries are always 5 participants and the treatment as usual condition has 5 participants while the active treatment has 4, then the staff randomizing the 10th participant will know with certainty that this participant will be in the active treatment group. To protect blinding, we have chosen to implement a variable boundary randomization for which the study staff randomizing patients will be blind to the boundaries and the resulting condition of the participant (see Sanghaei, 2011). The PI, Independent Evaluators, and Biostatistician will be blind to the condition of all participants until data lock. A research assistant overseeing randomization will also be blinded by randomizing unique patient identifiers into variable permuted blocks (through the STRONG STAR Data Core) by unique study identifier (e.g., first participant identified as #0001). All assessments given by Independent Evaluators will be labeled with just the unique identifier. Only the study coordinator (and co-coordinator) will be able to link unique identifiers to individual participants.

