- Participants will be randomly assigned into one of the two study arms (FORT-A, Treatment as Usual) on a 1:1 ratio. Participants will be randomized using variable sized blocks of an even number to maintain a balance within blocks. One weakness of block randomization is that blinded study staff who are aware of established block sizes will be able to predict, with increasing certainty, how a participant will be randomized as blocks fill. This does pose a threat to blinding and creates an opportunity for non-random assignment (e.g., cherry picking a participant who may be a particularly good responder to be “randomized” into the experimental condition). To maintain a blinded assignment schedule, we have chosen to work with the STRONG STAR Biostatistics and Data Core to execute the randomization schedule, hold the blinded assignments, and administer them to the study Coordinator sequentially during enrollment (i.e., the Coordinator and study team will always remain blinded to the next assignment)

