cohorts for FORT-A and PRC with between 3 to 7 participants (as described in Efrid, 2011). The coordinator and co-coordinator will be blinded to all randomization assignments but will initiate a treatment cohort when a sufficient number of participants have been assigned.

There is a four-week window between enrollment and baseline assessment (Week -4 to Week 0, as shown in 6.1). Study intervention must begin within 2 weeks after baseline to ensure that baseline assessment data adequately represent *current* functioning at the time of treatment, especially functional capacity evaluation [FCE] data that are used to guide the physical therapy portion of the interdisciplinary intervention. Test-retest reliability of FCE has been confirmed over a period of two weeks (Brouwer et al., 2003), with only slight fluctuations in more frequent testing resulting in a slight increase in lifting capacity if repeated across two days, likely due to practice effects (Reneman et al., 2002). Thus, intervention will generally begin within 5 weeks of enrollment.

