6.2.3 Blinding

Blinding in an interdisciplinary behavioral intervention is extraordinarily difficult since the intervention requires face-to-face contact and continuity of an interdisciplinary approach requires different interventionists to be able to talk to one another about patient progress. This is particularly true in trials of openly symptomatic conditions (like chronic pain; see Friedberg, Lipsitz, & Natarajan, 2010). There is no placebo control for an intervention like this (nor would the VHA allow one), so blinding is best accomplished through careful consideration of “need to know” privileging. Figure 2 provides a visual representation of who needs blinding and who is allowed to maintain awareness of patient identity. The entire study staff will be thoroughly briefed on the importance of maintaining blinding and the study coordinator will attend all study meetings and help ensure that blinding is maintained when blinded and unblinded personnel discuss the study participants. We have chosen to use a multi-level blinding scheme (as described by Friedberg et al.) in which study personnel will be blinded to randomized treatment **condition**, assessment **outcomes**, or **both** (as shown in Figure 2).

Study interventionists and their supervisors (for group psychosocial treatment; individual psychotherapy; biofeedback, and physical therapy) cannot be blinded to **condition** because they will be aware of the treatment condition of the patients they treat. Research Assistants (RA’s), blinded to participant identity, will listen to audio recordings of treatment sessions and will rate adherence to the treatment manual using a standardized checklist (see Section 10.3 Quality Assurance) for more information about this. The Research Coordinator and Co-Coordinator will be aware of participant condition (because they are responsible for randomizing and because they need to assist with adverse events monitoring and administrative oversight of treatment and assessment procedures), but they will be blinded to **outcomes**. The Coordinator and Co-Coordinator will not be directly involved in treatment or assessment and will be asked to only refer to participants by their unique identifiers when discussing participants with RA’s, the PI, or IE’s. Independent Evaluators will

become aware of outcomes during the course of their assessments, but will be blind to **condition** of the participants they assess.

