We will enroll $n = 65$ ($N = 130$) and anticipate $\leq 30\%$ all-source attrition rate as in our previous study. Assuming that at the 12-month follow-up the standard care treatment arm will report mean (SD) ODI scores of 19.5 (6.6), using a two-tailed $\alpha = 0.05$, we will have power = 0.80 to detect effect sizes as small as $d = 0.50$. For the ODI, this is equivalent to a clinically meaningful 3.3 point difference between groups. In our original FORT trial, we observed a 9.2 point difference between individuals who were not lost to follow-up at 12-months. Thus, for the intention-to-treat analyses, where we expect that up to 30% of individuals will require imputation of some kind, our expected effect sizes can be attenuated by $\sim 60\%$ with sufficient power to detect a clinically meaningful difference. Differences smaller than 3.3 points on the ODI are unlikely to be clinically meaningful.

Treatment Assignment Procedures

Participants will be randomly assigned to each of the study arms based on the rationale and procedures outlined in sections 6.2.2 and 6.2.3 of this protocol. Masking will be managed using the diagram shown in Figure 2. Pursuant to this diagram, masking will be overseen and maintained through a collaboration between the study coordinator (who will not be blind to any part of this study to all for better tracking of participant flow and AEs; though the Coordinator will not take part in any evaluations and is forbidden to discuss blinded information with any study team member without first discussing it with the PI and the STRONG STAR Administrative Core) and the STRONG STAR Data Core (which maintains the link between identity and participant number). Masking of treatment arm to the participant or provider is absolutely impossible in a behavioral trial. Plans for

retention of the blind are described in sections 5.2, 5.4, and 6.2.3.1 of this protocol. If a blind must be broken (e.g, to protect the safety of a participant), then the blind can only be broken by the study Coordinator and/or Co-Coordinator after consultation and permission from the PI and the STRONG STAR Admin Core. To break the blind, the Coordinator will contact the STRONG STAR Data Core and request revelation of the participant identity and linked unique identifier.

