Medication Data will be adjudicated by the PI, the Research Coordinator, and [name] (an expert in trauma and addiction comorbidity). Timeline followback interview and MQS-III data will be discussed for each participant by the IE and the Coordinator within two business days of each assessment. If there are any noted problems with the TLFB data, then the assessment will be adjudicated by the above sub-committee within 2 days of review. MEMS cap data will be gathered for each participant's reported "most helpful" pain medication and any opioid medications they are prescribed by VA or other providers outside the VA system during the course of the study. MEMS data will be downloaded for each participant at each assessment follow-up visit. Upon download, the IE will scrutinize downloaded data to ensure that it falls within an expected range. If aberrant or missing data are noted, these will be adjudicated with the above sub-committee (and potentially discussed with the manufacturer if hardware or software problems are suspected) in a deidentified format.

The primary opioid endpoint will be the timeline followback (TLFB) interview. The TLFB represents the primary measure of opioid use because of its reliability and sensitivity as a daily measure of opioid use and its lack of perceived stigma compared to regular urine tox screen. A trained and masked IE will administer TLFB asking participants about any opioid medication use and use of other medications for pain. The TLFB Interview for this study was adapted from Sobell and Sobell (1992) as a semi-structured clinical interview asking the participant to use a blank calendar to describe the number of pain pills taken each day for 30 days. Instructions are provided to help the interviewer guide the participant in completing the recall as accurately as possible. This method has been reliably used in other trials of medication/opioid use and abuse (Kunoe et al., 2009).

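### Secondary outcomes are reviewed, recorded and adjudicated by staff who know, or may know, the arm, against the plan's own blinding rules

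*Combined protocol and SAP*

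**What the plan says.** **Coordinator.** Section 6.2.3 states that "The Research Coordinator and Co-Coordinator will be aware of participant condition", that they are blinded to outcomes, and that "The Coordinator and Co-Coordinator will not be directly involved in treatment or assessment". Section 9.2 describes the Coordinator as someone "who will not be blind to any part of this study" who takes no part in evaluations and who "is forbidden to discuss blinded information with any study team member" unless the PI and the Administrative Core have been consulted first. Section 6.2.2 says "The coordinator and co-coordinator will be blinded to all randomization assignments". Section 4.3 says only that "the Coordinator and study team will always remain blinded to the next assignment", which may be all that Section 6.2.2 means. Section 9.5.2 then provides that TLFB and MQS-III "data will be discussed for each participant by the IE and the Coordinator within two business days of each assessment". It also names the Coordinator as an adjudicator of medication data and physical measures, and Section 9.5.1 does the same for unclear ODI responses.

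**FCE and Actiwatch.** Section 6.2.3.1 says that only IEs complete outcome assessments, and Section 10.1 says that an IE blind to condition collects the data. Section 9.5.2 has FCE recorded by PT students and/or PRC PT/OT providers. Ambiguous FCE and Actiwatch data go to a sub-committee of the PI, the PT interventionist(s), and a PT expert or PRC PT/OT. Section 5.2 names PT students and PRC PT/OT staff as providers of FORT-A physical therapy, and Section 6.2.3 says that interventionists and their supervisors cannot be blinded.

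**PI.** Section 3 keeps the PI blind until data lock. Section 7.1 has pain of 8-10 after study PT discussed with the PI by unique identification number. Sections 9.5.1 and 9.5.2 use the same unique identifier for outcome adjudication.

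**The concern.** Participants and therapists cannot be masked in this trial, so protection against assessment bias rests on who collects, reviews and settles the data. TLFB is the main measure for Aim 2, and FCE is the objective disability measure under Hypothesis 2. A reviewer who knows the arm can influence which TLFB entries are questioned and how a doubtful one is resolved. A tester who knows the arm can influence encouragement or scoring on a performance test. If the plan does not say who is blind, a report that these outcomes were assessed blind cannot be defended.

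**Working it through.** No power or effect-size calculation applies. The check sets the sections against each other, with counts for frequency.

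1. **Coordinator's knowledge of arm.** Section 6.2.3: aware. Section 9.2: blind to nothing. Section 6.2.2: blind to all assignments. Reading Section 6.2.2 in the light of Section 4.3 (blind to the next assignment only) makes these three agree that the Coordinator knows the arm of participants already randomized.

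2. **Coordinator's access to outcomes.** Section 6.2.3 excludes outcomes and assessment. Section 9.5.2 requires a discussion of each participant's TLFB and MQS-III data after each assessment, so access is routine and not confined to problem cases. No reading of Section 6.2.2 removes this conflict. A standing discussion with a blinded IE also sits badly with Section 9.2, which requires prior clearance before blinded information is discussed.

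3. **Do unique identifiers mask these people?** Section 3 says "Only the study coordinator (and co-coordinator) will be able to link unique identifiers to individual participants". Section 9.2 has the Data Core maintain the link. Section 10.1 gives the Coordinator and the interventionists as examples of staff with access to it. The three differ, but on Section 10.1 neither the Coordinator nor the PT interventionists are masked by an identifier. Nor can an identifier mask a tester who meets the participant.

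4. **FCE.** Sections 6.2.3.1 and 10.1 (blinded IEs) conflict with Section 9.5.2 (PT students and PRC PT/OT providers). For recording, the documents show overlap of staff groups. For adjudication the overlap is explicit, because the PT interventionists are members.

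5. **PI.** Section 7.3 specifies pain ratings at each PT appointment for FORT-A participants, and under Section 5.1.1 the research gives the comparison arm no further PT recommendation. A report of high pain after study PT under a unique identifier can therefore reveal the arm, and the PI later adjudicates outcomes under that identifier.

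6. **Frequency.** Section 9.2 gives 12 TLFB administrations. Counting every occasion in Sections 6.1, 6.2.4 and 6.2.5 separately from baseline on: baseline 1 + post-treatment 1 + phone 11 + six-month 1 + 12-month 1 = 15, of which 14 follow baseline. FCE is scheduled 4 times, 3 of them after treatment. These count occasions for discussion or testing, not values set by arm-aware staff.

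7. **Scale of one decision.** Recidivism is a threshold of 3 days of opioid use in 30 (Sections 3 and 9.6), so one disputed day can change a participant's status. With 65 per arm and none lost, one changed status moves that arm's rate by 1/65 = 0.015, about 1.5 percentage points. How often this would happen is not stated and cannot be derived.

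**The case against.** The strongest reply is that the data are well protected where it counts. A masked IE administers TLFB and ODI. Data are double-entered and paper forms uploaded (Section 10.1), which applies to study data generally and leaves a record against which changes can be checked. About 10% of recordings are reviewed by a non-study assistant (Section 5.4), and MEMS, CPRS and PAT give independent checks on opioid use. Section 9.5.2 says the data are discussed; it gives the Coordinator no power in that discussion to alter an entry. All of this stands and limits the risk. It does not reconcile the sections, and it does not address a treating therapist's vote on FCE.

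Several stronger readings are tempting but not supported:

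- **That therapists test their own patients.** Only group overlap is shown. There are to be more than 2 student therapists (Section 5.2), and no section says that one person treats and tests the same participant.
- **That no rule separates treating from testing staff.** This can be said only of the visible text. Figure 2 is not shown, and the PT manual of procedures was still being written.
- **That staff meetings unblind the PI.** Section 5.2 plans meeting identifiers distinct from the research number, and the case numbers in Section 6.2.3.1 may be those. The plan itself doubts that they are workable, and they do not cover the safety reports in Section 7.1.
- **That the primary ODI result is compromised.** Section 9.5.1 says ODI adjudication is almost never needed.

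A practical objection also has force. The trial was planned for 2014-2019 and version 10.0 is dated September 2019, so reassigning roles may reach few remaining assessments.

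**Conclusion.** The plan contradicts its own blinding rules for secondary outcomes in three places: the Coordinator's routine review of TLFB/MQS data and membership of the adjudication groups, the recording and adjudication of FCE (with Actiwatch adjudication), and the identifier shared between safety reports to the PI and outcome adjudication. The first two are direct conflicts of current text. The third is a route by which the PI's blind can fail. A reader might infer that the TLFB or FCE results are biased; the documents show the opportunity, not its effect. The size cannot be computed because no rate of queries or adjudications is given for these outcomes. The consequence for the primary ODI analysis is likely negligible. The conclusion assumes that Sections 6.2.3 and 9.2 describe the Coordinator's actual knowledge of arm, and that Figure 2 and the procedures not shown do not override the written text.

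**What to change.** 1. State one blinding status for the Coordinator. Give TLFB/MQS review and all outcome adjudication to existing evaluators confirmed blind to arm, with the Coordinator only de-identifying materials. If staffing does not allow this, disclose that the review was not blind.
2. Remove from FCE and Actiwatch adjudication the PT interventionist(s) and any PRC PT/OT who delivers or supervises FORT-A physical therapy. Have follow-up FCE recorded by existing PT staff who are not treating that participant; otherwise state that FCE is unblinded and interpret it so. Baseline FCE can still go to the treating therapists, who need it under Section 6.2.2.
3. Use adjudication identifiers different from those in safety reports, or take the PI out of outcome adjudication. Leave safety reporting unchanged, and do not claim that this makes the PI fully blind.
4. Reconcile Sections 3, 6.2.2, 6.2.3, 6.2.3.1, 7.1, 9.2, 9.5.1, 9.5.2 and 10.1.
5. For data already collected, report which outcomes were recorded, reviewed or adjudicated by staff who knew the arm.

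The cost is reassignment of existing roles, a second identifier list and some FCE scheduling effort. It adds no visits or measures. Numbers of evaluators and FCE testers are not given, which is why items 1 and 2 carry a disclosure fallback.
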